#### 8.2.1 Hematologic Toxicity

Hematologic values outside of the normal reference range are inherent features of MPNs and are expected effects of many therapeutic attempts to manage these diseases. MPN patients require doses of bomedemstat that are sufficient to reduce platelet counts and, to a lesser degree, absolute neutrophil counts. Any resulting reversible cytopenias can be managed clinically as needed with transfusions as well as broad-spectrum antibiotics, as *per* standard practice.

The effects of bomedemstat on normal myeloid hematopoiesis observed in non-clinical and clinical studies are expected; these are pharmacodynamic effects of LSD1 inhibition by bomedemstat, thus not regarded as adverse. Refer to the Investigator's Brochure for additional information.

#### 8.2.2 Stopping Rules

Bomedemstat will be permanently discontinued and the patients will undergo the Follow-up Period visits (see Section 9.4) in the event of the following:

- PI or Medical Monitor deem it unsafe for the patient to continue bomedemstat.
- Following the temporary interruption of bomedemstat due to platelet counts below the applicable threshold ( $25 \times 10^9/L$  for MF patients and  $50 \times 10^9/L$  for ET patients), the patient's platelet counts do not return to the required threshold ( $>50 \times 10^9/L$  for MF patients and  $>150 \times 10^9/L$  for ET patients) within 21 days. Note: new platelet thresholds may apply as additional feeder studies are conducted; such thresholds will be specified in the Study Reference Manual and Pharmacy Manual.

#### 9 STUDY ASSESSMENTS

This section provides comprehensive detail on the visits and assessments required and should serve as the main guidance for use during study visits. The Schedule of Assessments (Section 16.1) contains these details in tabular form and is provided for use in a supportive/reference capacity only. To maintain clarity while facilitating a modicum of brevity, the 'Terms' in Table 1 below will be utilized in this section to encompass the broader 'Protocol Meaning' as stated.

Table 1 List of Protocol Terms and Meanings

Town			
Term	Protocol Meaning		
Limited Physical Exam, including Vital Signs	• Spleen measurement. The edge of the spleen shall be determined by palpation, measured in centimeters, using a soft ruler/tape, from the costal margin to the point of greatest splenic protrusion in the midclavicular line. Measure in the same manner at all visits.		
	Weight, measured (in kg)		
	Review of body systems for changes from previous visit		
	• Vital signs, after patient has sat semi-supine for ~3 minutes, of:		
	o Heart rate		
	o Respiratory rate		
	
 
Temperature
 
		
	
 
Systolic/diastolic blood pressure
 
		
Adverse Events and Concomitant Medications Collection	Use non-directive questions (i.e., "How are you feeling") to query patient regarding AEs that may have occurred and inquire about medication changes.		
Full Local Lab Assessment	The following panels performed locally (Section 10.1.1 details analytes):		
	Hematology with automated differential		
	Biochemistry		
	Coagulation		
	Urinalysis		
	Serum pregnancy test for WOCBP		
MPN Symptom Questionnaires	IRB/EC approved questionnaires will be completed based on the version required in the applicable feeder study. For example, the MPN-SAF TSS for IMG-7289-CTP-102 and the MPN-SAF for IMG-7289-CTP-201.		
	Questionnaires will be completed weekly, ideally at the same time and day each week for consistency, through the EoS or ET Visit. The actual date of questionnaire completion, not the planned or collected date, must be documented on each questionnaire completed. On visit days, the questionnaire should be completed prior to the study visit. If the patient arrives without a completed questionnaire, the patient will complete it during the visit, and it will be collected by study staff prior to the patient departing.		

Term	Protocol Meaning	
	Importantly, multiple questionnaires will need to be provided to the patient for completion on a weekly basis between visits. Note, for patients undergoing monthly labs locally, consideration should be given to the use of a courier for provision and return of questionnaires.	
Bone Marrow Sampling and Assessments	
 
Aspirate sample should be optimally obtained within the first pull. Do not collect after a second pull attempt, and biopsy collected as per site standard procedure.
 
A central laboratory will perform morphology
 
	
	review, fibrosis grading and store BMMCs for possible correlative research analysis (Section 10.1.2).	
	
 
Note: Any results available from site routine bone marrow work-up, including morphology, cytogenetics, other genetic interrogations will be collected either via the eCRF or through collection of local reports.
 
	
Study Drug Dispensing and Dosing Instructions	Administer bomedemstat in accordance with the Pharmacy Manual instructions.	
	• Instruct patients to refer to their Dosing Card every day for details on bomedemstat dosing (Section 7.2.2) and handling of missed doses (Section 7.2.4)	

**Note:** If at any time additional clinical evaluation outside of the visit schedule is deemed necessary by the Investigator, then unscheduled visits should occur, and data should be collected.

## 9.1 Enrollment Period

[figure not shown]
#### 9.1.1 Informed Consent Visit

Details of the extension study and a copy of the Participant Information Sheet/Consent Form (PISCF) should be provided to the patient prior to their anticipated final feeder study visit. Informed consent should be obtained at, or before, the feeder study's final visit. Patients must provide documented informed consent before undergoing any study-related procedures. The PI, or designee, will explain to the patient the study purpose, the risks and benefits involved and that their participation is voluntary. Each patient will acknowledge receipt of this information and that they wish to participate in the study by giving documented informed consent for their involvement in the study in the presence of the PI, or designee, who will also sign and date the PISCF. Time, date, name of the person taking consent and any questions raised by the patient must be documented in the source data.

[figure not shown]
## 9.1.2 Eligibility Assessment

Once consent has been obtained for participation in the extension study, the PI will assess whether the patient is eligible. If the patient meets all eligibility criteria, then they will be enrolled upon commencement of their first extension study visit (Section 9.1.4). Patients deemed ineligible should have the reason(s) documented in the patient's source data and on the Screening & Enrollment log.

[figure not shown]

[figure not shown]

## 10 LABORATORY SAMPLING FOR SAFETY AND PD ANALYSIS

Blood, bone marrow and/or their contents may be retained for future exploratory studies.

The average of the blood volumes collected, which varies by local laboratory institution, is provided in EC/IRB approved the informed consent.

See Section 10.1 and 10.2 for the specifics and volumes required for each test.

## **10.1 Laboratory Measures**

Details on the laboratory assessments performed throughout the study are provided below by category of tests (i.e., biochemistry, hematology, etc.). Details on the specific laboratory assessments required at each visit are located in Section 9 and in schematic form in Appendix 16.1. When each category of test is required, at a minimum, the following clinical laboratory determinations (or their equivalent) will be performed. Exceptions are noted by asterisk (\*) to reflect that the particular analyte will only be analysed if the test is available at the particular institution.

## **10.1.1 Local Laboratory Measures**

**Biochemistry**: Serum creatinine, uric acid, urea\* or blood urea nitrogen (BUN)\*, albumin, total bilirubin, gamma glutamyltransferase (GGT), alkaline phosphatase (ALP), alanine aminotransferase (ALT), aspartate transaminase (AST), lactate dehydrogenase (LDH), C-reactive protein (CRP) and serum ferritin.

*Hematology*: Hemoglobin, red blood cell count (RBC) (including nucleated RBC), red cell distribution width, hematocrit, mean corpuscular volume (MCV), mean corpuscular haemoglobin (MCH), mean corpuscular haemoglobin concentration (MCHC), platelets, mean platelet volume (MPV)\*, white cell count and automated or manual assessment as needed to ensure the following results are generated: neutrophils, lymphocytes, monocytes, eosinophils, basophils, reticulocytes, promyelocytes, myelocytes, metamyelocytes and blasts.

**Coagulation**: Prothrombin time (PT)\*, activated partial thromboplastin time (aPTT) and International normalized ratio (INR).

**Serum Pregnancy Test**: For WOCBP, a serum pregnancy test will be utilized according to institution standard procedure. The result must be confirmed prior to next scheduled dose of bomedemstat.

*Urinalysis*: Leucocyte esterase, nitrites, urobilinogen, protein, pH, blood, specific gravity, ketones, bilirubin and glucose.

**Bone marrow sampling:** At each sample time-point both aspirate (unless there is a dry tap) and biopsy samples are required to be obtained as per site standard procedure. Evaluation of morphology including fibrosis score will be performed centrally (see Section 10.1.2);. Additionally, any locally available cytogenetic or genetic interrogations performed on samples obtained at the same time-point as study samples will also be reported in the eCRF or collected *via* local lab reports.

Additional Tests for Italy: HIV test, HAV, HBsAg, HBsAb, HBcAb, HCV

*Sample Processing*: Sponsor will not provide either a laboratory manual or study supplies for the collection and handling of samples to be analysed locally. Local laboratory standard procedures should be followed at each site.

**Blood sample volume:** The volume of blood needed to perform a Full Local Laboratory Assessment and a Hematology Local Laboratory Assessment varies by institution.

## **10.1.2 Central Laboratory Measures**

**Bone Marrow Sampling Requirements:** Approximately 2-3 mL bone marrow aspirate sample for central analysis must be collected from the first pull, whenever possible, and no later than the second (except in the case of dry tap). A peripheral blood smear must also be provided the same day for review in conjunction with the bone marrow sample; additionally a de-identified copy of the hematology (CBC) report from the day of bone marrow sampling should be sent to the central lab with the bone marrow samples (or follow by email as soon as available). A 1-2 cm section of

trephine bone marrow sample must also be collected and sent to the central laboratory as a formalin fixed, paraffin embedded block (unless alternative arrangements have been agreed with sponsor). Measures to be performed centrally include: myelofibrosis grading and morphology review. Remaining bone marrow aspirate following preparation of the morphology slides may be used for analysis of mutant allele burden over the course of bomedemstat treatment. Genomic sample collection, handling, storage, and analysis will conform to all applicable national guidance and regulations.

*Genomic Testing:* At each required sample time-point approximately 20 mL peripheral blood sample will be collected for analysis. During the feeder protocols germline samples consisting of hair roots and a cheek swab were collected for analysis. If, upon analysis, the sample yield was found to be inadequate a repeat sample of either type may be requested as part of their feeder study or as part of this protocol. Genomic sample collection, handling, storage, and analysis will conform to all applicable national guidance and regulations.

**Future Correlative Studies:** Approximately 10 mL additional blood will be collected and stored in conjunction with each genomic blood sampling time-point for the purposes of potential correlative studies. If site process permits, samples collected and stored earlier in the course of their MPN, and any available genetic data may be requested.

Patients at specific sites/countries may need to provide specific consent for the analysis of these correlative samples but samples will be collected for all patients.

**Sample Processing**: Sponsor will provide a laboratory manual documenting the collection and handling of samples to be analysed centrally. Laboratory supplies will be provided for the collection of all central laboratory samples.

[figure not shown]

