# **Efficacy**

In **all patients**, efficacy will be assessed by evaluation of:

- Constitutional symptoms measured by continued completion of the version of the MPN-SAF tool associated with the feeder study
- Formal measures of response, including relapse, and disease transformation
- Fibrosis score

In **MF patients**, efficacy will also be assessed by:

• Spleen volume reduction

In **ET patients**, efficacy will also be assessed by:

- Patient reported change in clinical status as measured by the PGIC
- Durability in the reduction of platelet counts in the absence of new thromboembolic events
- Durability in the reduction of white blood cell count
- Evaluation of the incidence of thromboembolic events

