#### 12.3 Treatment Assignment and Blinding

This is an open-label study. The Investigators, other hospital personnel, patients and Sponsor will know the identity of the treatment.

Effort will be made, as appropriate, to maintain continuity of study staff who administer/evaluate various assessments at each site (i.e., physical examination, morphology/fibrosis grade review, etc.), in order to facilitate consistency of assessments within a patient.

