### 16.3 Eastern Cooperative Group Performance Status

Grade	ECOG Performance Status	
0	Fully active, able to carry on all pre-disease performance without restriction	
1	Restricted in physically strenuous activity but ambulatory and able to carry out work of a light or sedentary nature, e.g., light house work, office work	
2	Ambulatory and capable of all self-care but unable to carry out any work activities; up and about more than 50% of waking hours	
3	Capable of only limited self-care; confined to bed or chair more than 50% of waking hours	
4	Completely disabled; cannot carry on any self-care; totally confined to bed or chair	
5	Dead	

Semiquantitative grading of BM fibrosis with minor modifications concerning collagen and osteosclerosis. Fiber density should be assessed only in hematopoietic areas.

<sup>aIn grades MF-2 or MF-3 an additional trichrome stain is recommended.

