	Leukaemic transformation confirmed by a bone marrow blast count of ≥20% or
	A peripheral blood blast content of $\geq$ 20% associated with an absolute blast count of $\geq$ 1 x 109/L that lasts for at least 2 weeks
Stable disease	Belonging to none of the above listed response categories
	No longer meeting criteria for at least CI after achieving CR, PR, or CI, or
Relapse	Loss of anaemia response persisting for at least 1 month or
	Loss of spleen response persisting for at least 1 month

EMH, extramedullary haematopoiesis (no evidence of EMH implies the absence of pathology- or imaging study-proven non-hepatosplenic EMH); LCM, left costal margin; UNL, upper normal limit.

\*Baseline and post-treatment bone marrow slides are to be interpreted at one sitting by a central review process.

†Grading of MF is according to the European classification Thiele et al. European consensus on grading bone marrow fibrosis and assessment of cellularity. It is

Imago BioSciences, Inc., a subsidiary of Merck & Co., Inc. Bomedemstat (IMG-7289/MK-3543)

underscored that the consensus definition of a CR bone marrow is to be used only in those patients in which all other criteria are met, including resolution of leukoerythroblastosis.

‡Immature myeloid cells constitute blasts + promyelocytes + myelocytes + metamyelocytes + nucleated red blood cells. In splenectomized patients, <5% immature myeloid cells are allowed.

§See above for definitions of anaemia response, spleen response, and progressive disease. Increase in severity of anaemia constitutes the occurrence of new transfusion dependency or a  $\geq 20$  g/L decrease in haemoglobin level from pretreatment baseline that lasts for at least 12 weeks. Increase in severity of thrombocytopenia or neutropenia is defined as a 2-grade decline, from pretreatment baseline, in platelet or absolute neutrophil count, according to the Common Terminology Criteria for Adverse Events (CTCAE) version 4.0. In addition, assignment to CI requires a minimum platelet count of  $\geq 25000 \times 10^9$ /L and absolute neutrophil count of  $\geq 0.5 \times 10^9$ /L. ¶Applicable only to patients with baseline haemoglobin of < 100 g/L.

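### Central fibrosis grading: the laboratory receives the same-day blood counts and no visible text masks slide order or time point, so reader expectation could contribute to apparent improvement

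*Combined protocol and SAP*

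**What the plan says.** Section 10.1.2 sends three things to the central laboratory: the marrow, a blood smear and the day's blood counts. On the smear: "A peripheral blood smear must also be provided the same day for review in conjunction with the bone marrow sample". On the counts: "a de-identified copy of the hematology (CBC) report from the day of bone marrow sampling should be sent to the central lab", with the option of emailing the report later. The same section states: "Measures to be performed centrally include: myelofibrosis grading and morphology review". Section 10.1.1 likewise treats the fibrosis score as part of one central morphology evaluation.

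The MF response criteria in 16.4 carry a footnote to the marrow component: "Baseline and post-treatment bone marrow slides are to be interpreted at one sitting by a central review process". The ET criteria in 16.5 have no equivalent.

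The Synopsis, under Criteria for Evaluation, lists "Fibrosis score" among the efficacy measures for all patients. Section 12.5.2 summarises the exploratory endpoints from feeder-study baseline onward, with no comparator. Section 12.3 says "The Investigators, other hospital personnel, patients and Sponsor will know the identity of the treatment" and asks for continuity of assessors, naming fibrosis review as one example. It sets no masked-reader rule.

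**The concern.** The MF-0 to MF-3 scale in 16.2 is described there as semiquantitative, so borderline slides are settled by judgement. A reader who knows which slide is baseline and which is on treatment, and who can see the counts, has a direction in which to resolve them. The protocol itself supplies that direction: Section 3.3 reports near-complete clearing of reticulin fibrosis in treated mice. Removing the patient's identity from the count report does not remove the counts.

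At stake is the interpretation of any fibrosis improvement, which bears on the objective concerning long-term effects on the course of MF and ET. Without a control arm, a tendency to read follow-up slides as better cannot be separated from a drug effect after the fact.

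**Working it through.** The plan gives no figure to reproduce: Section 12.2 states that there is no sample size calculation, and no fibrosis test is visible. The check is first textual, then illustrative.

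**1. Do the counts reach the grading laboratory?** Yes, by 10.1.2. That the individual grader sees them before grading is an inference. It is a reasonable one, because smear and marrow are reviewed together and 10.1.1 treats fibrosis as part of the morphology evaluation.

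**2. Is anything masked?** Nothing is stated in Table 1 of Section 9, 10.1.1, 10.1.2, 12.3, 16.2, or the footnotes to 16.4 and 16.5. These are the places where such a rule would be expected.

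**3. Do the counts carry information?** Section 3.5 says platelets are the most sensitive lineage and that monocytes rise. Section 3.6.1 gives feeder-study platelet targets of 50-75 × 10^9/L (MF) and 200-400 × 10^9/L (ET). The counts therefore indicate how far the drug has acted.

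**4. Are the counts needed for the grade?** The definitions in 16.2 use reticulin, collagen and osteosclerosis, and its table note adds: "Fiber density should be assessed only in hematopoietic areas". None of this refers to blood counts. They serve the morphology review.

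**5. Can one grade decide a response?**

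| Category | Fibrosis condition | Platelets (× 10^9/L) |
|---|---|---|
| MF complete response | grade 1 or lower | at least 100 |
| MF partial response, route without marrow | none | at least 100 |
| MF partial response, marrow route | grade 1 or lower | 50 to below 100 |
| ET complete remission | nothing above grade 1 | 400 or lower |

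An MF patient held at the feeder-study target of 50-75 meets the platelet condition of the marrow route only. For that patient a call between grade 1 and grade 2 can decide whether a partial response is possible.

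**6. Illustration (assumed inputs, not document values).** Suppose there is no true change. Let d be the chance that two reads of a pair differ by at least one grade, and s the share of those differences called improvement.

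- Apparent improvement = d × s
- Apparent worsening = d × (1 − s)
- Net = d × (2s − 1)

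| d | Net at s = 0.6 | Net at s = 0.8 |
|---|---|---|
| 0.10 | 0.10 × 0.2 = 2 points | 0.10 × 0.6 = 6 points |
| 0.20 | 0.20 × 0.2 = 4 points | 0.20 × 0.6 = 12 points |
| 0.30 | 0.30 × 0.2 = 6 points | 0.30 × 0.6 = 18 points |

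Widening the inputs to d = 0.40 and s = 0.9 gives 0.40 × 0.8 = 32 points, which shows how strongly the result follows the inputs. At s = 0.5 the net is 0 for any d.

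Example: d = 0.20 and s = 0.80 give 16% improved and 4% worse. If all of the roughly 80 patients had an evaluable pair, 80 × 0.16 = 12.8, about 13. The Clopper-Pearson 95% interval for 13/80 is 8.9% to 26.2%. It expresses sampling error only and does not reflect the reading bias.

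**The case against.** The case against is substantial, and much of it stands as a limit on the point.

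- **Silence is not a rule.** The text of 12.4.2, parts of Section 9 and the ET list in 12.5.2 are removed. The SAP to which 12.1 defers and the central laboratory manual are not in the document set. A masking rule could sit in any of these. The manual is, however, described in 10.1.2 as covering collection and handling. If a rule exists, a cross-reference settles the matter.
- **Who sees the counts, and when.** A reader might infer that the grader always has the counts in hand. The documents name the laboratory as recipient and let the report follow later, so this is likely but not stated.
- **Scope of the paired read.** A reader might infer that every marrow is read in an unmasked pair. The one-sitting rule belongs to the MF response criteria only. Paired central reading is itself sound, since it limits drift between reads. The gap is the absent masking of order.
- **The counts are not the main clue.** Every patient has already completed a Treatment Period in a feeder study (6.1.1), so every marrow taken here is post-treatment. Withholding the counts alone would mask little, and order and time point must be masked as well.
- **Masking is imperfect.** Section 3.5 says the drug alters marrow composition and cell morphology, so a coded slide may still reveal treatment. A claim that masking would bring the bias to zero is not supported. Nor is masking the only safeguard, since central grading and explicit grade definitions already exist.
- **The illustration is simplified.** It ignores floor and ceiling: MF-0 cannot improve and MF-3 cannot worsen.
- **Counts have a use.** Section 3.5 warns that the changes may be unfamiliar to haematopathologists. This supports releasing the counts for morphology, but not before the grade is recorded.

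**Conclusion.** The point holds as a worthwhile improvement. The stated workflow supplies blood counts to the grading laboratory and has MF pairs read together without stated masking. That permits reader expectation to enter a visual efficacy measure for which there is no control arm.

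The size is unknown. The 2 to 18 points above rest wholly on assumed discordance (0.10 to 0.30) and assumed direction (0.6 to 0.8), and should be cited only as an illustration of scale.

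A reader might go further and infer that fibrosis results will be biased, or that the study's main conclusion is at risk. The documents support neither. Primary endpoints are safety (12.4.1), and no fibrosis test is visible, so type I error and power are not at issue. What is affected is how far a reported fibrosis improvement, or a response that depends on it, can be attributed to the drug. The conclusion also assumes that no masking rule exists in the removed text, the SAP or the laboratory manual.

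**What to change.** **Section 10.1.2.** State that the central reader records and locks the fibrosis grade before the count report, smear and clinical data are released for the morphology review.

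**Section 16.4.** For the one-sitting MF read already required, state that slides are coded and that baseline and follow-up are presented in random order without dates or time points. Use that grade for the fibrosis efficacy summary and for MF response.

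**ET.** Apply the same coded paired read where feeder-study baseline slides are available.

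**Timing.** State that reads needed promptly for suspected relapse or Day 169 qualification keep their current timing and do not wait for a batched sitting.

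**Cost.** Slide coding, one handling step before the morphology report, and retrieval of feeder-study baseline slides, to which the documents state no access arrangement. Because Treatment Periods repeat, baseline slides will be re-read more than once or follow-up slides batched for the efficacy read. No extra reader, sample or patient procedure is needed. If a masking rule already exists in the SAP or laboratory manual, a cross-reference in 10.1.2 is enough.
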